## 8.0 TIMEFRAME OF MEASUREMENTS AND DATA COLLECTION

	TTE	TEE	MRI	QOLq	HFq	6MWT	Blood
Screening	x						
Pre-op	x	X*	X*	0	0	0	0
Intra-op		x					
Chest closure		x					
Discharge	x						0
30 days	x						0

6 months	0			0	0	0	0
12 months	0	0*	0*	0	0	0	0

**x:** indicates current standard of care  
**0:** indicates non-standard of care, paid by the study  
**\***: indicates that both procedures could be performed, or only one of them, depending on what is practically possible and what the patient agrees to undergo.

**TTE:** trans-thoracic echo  
**TEE:** trans-esophageal echo  
**MRI:** magnetic resonance imaging  
**QOLq:** quality of life questionnaire  
**HFq:** heart failure questionnaire  
**6MWT:** 6-minute walk test  
**Blood:** blood collection for laboratory studies

## 9.0 DEFINITIONS AND MEASUREMENT OF ENDPOINTS

Primary Endpoints:	The primary endpoint of this study is to investigate if pre-operative inter-papillary muscle separation (diastolic, systolic and diastolic-systolic) correlates with FMR severity at 12 months after surgery with UMA and UMA+PMA.
Secondary Endpoints:	
Survival
 
 
• All-cause mortality at discharge, 6 months and 1 year
 
 
Functional Status and Hospitalizations
 
 
• MACE MACE is defined as a non-weighted composite score comprised of the following: 
 
- Death
 
- Stroke
 
- Worsening heart failure (+1 NYHA class)
 
- CHF hospitalization
 
- Mitral valve re-intervention
 
 
 
• NYHA classification Functional status will be assessed by the NYHA classification scale. (Appendix 1)
 
• 6-minute walk test Functional status will also be measured by a 6-minute walk test, which assesses the distance walked (in feet) during the pre-specified time period. The test will be administered by a trained study coordinator. (Appendix 2)
 
• Readmission rates
 

Readmission rate will be calculated for any cause within the first 30 days and for all cause, cardiovascular and heart failure after 30 days following surgery. Classification of readmission as heart failure related requires at least 2 out of the following signs and symptoms of acute decompensated heart failure:

- Dyspnea felt related to HF
- Treatment with intravenous diuretic, vasodilator or inotropic therapy
- X ray evidence of pulmonary edema or pulmonary vascular congestion
- Rales on physical exam
- PCWP or LVEDP > 18mm Hg

All readmissions will be classified by the investigator and adjudicated by the event adjudication committee.

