	
Intracardiac pressures and hemodynamics, including pulmonary artery pressures and pulmonary capillary wedge pressure will be assessed by Doppler flow studies.
 
Regional Wall Motion (LV function and viability assessment) will be assessed at baseline and again at one year following surgery.
 
Inter-papillary muscle separation (IPMS) is measured as the distance between the centers of the antero-lateral papillary muscle and postero-medial papillary muscle in a short axis echo plane. IPMS will be measured at three locations: papillary muscle tips, mid-body and base. IPMS will be measured in each frame of the cine loop, optimized to obtain at least 20 frames per heart beat. IPMS is reported in diastole, systole and differences between diastole and systole.
 
 
• Cardiac MRI parameters
 
 
Late-Gadolinium enhanced cardiac MRI will be performed on all patients pre-operatively. Standard protocols will be used to obtain 2 and 4 chamber gated images of cardiac chambers.
 
Presence and severity of mitral regurgitation will be measured as (total stroke volume (EDV-ESV)) – (aortic forward ejection (measured using flow encoded MRI imaging at the aortic valve annulus)). Measurements will be obtained using flow encoded MRI at the mitral annular plane as well.
 
LV size, geometry and function will be assessed by the following measures: LV dimensions, ejection fraction (segmenting LV from short axis and rotated long axis images), LV end-systolic volume index using the biplane volumetric method, LV mass, LV sphericity, strain, and twist.
 
Regional Wall Motion (LV function and viability assessment) will be assessed at baseline and again at one year following surgery.
 
Inter-papillary muscle separation (IPMS) is measured as the distance between the centers of the antero-lateral papillary muscle and postero-medial papillary muscle in a short axis echo plane. IPMS will be measured at three locations: papillary muscle tips, mid-body and base. IPMS will be measured in each frame of the cine loop, optimized to obtain at least 20 frames per heart beat. IPMS is reported in diastole, systole and differences between diastole and systole.

--	---

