## 11.0 ANALYSIS PLAN

**General design issues:** This is an observational, prospective, non-randomized, single center, multiple phase study. Enrolled patients will have clinically significant FMR with either ischemic or non-ischemic cardiomyopathies. 50 patients are recruited to phase 1 (all 50 receiving undersizing mitral annuloplasty), and 90 patients to phase 2 (75 receiving undersizing mitral annuloplasty and 15 receiving undersizing mitral annuloplasty and papillary muscle approximation). In patients

receiving undersizing mitral annuloplasty, the same rigid annuloplasty ring will be used as consistently as possible, and up to two sizes of downsizing will be performed as consistently as possible. In some patients recruited to the study, the surgeon may decide to switch to mitral valve replacement, or may perform a repair and deem it to be a failure and then switch to mitral valve replacement. In either case, the patient will continue to be part of the study, but with follow-up performed only at 12 months.

**Sample size estimation and statistical analysis plan:** The primary objective of this study is to determine the correlation between pre-operative inter-papillary muscle separation and the 6 month and 12 month post-operative FMR grade after undersizing mitral annuloplasty. Pre-operative inter-papillary muscle separation will be measured and is a continuous variable, while the recurrence of FMR will be deemed binary (1: if MR greater than or equal to 2+ severity observed at 12 months; 0: if MR less than or equal to 2+ severity observed at 12 months). An ROC curve analysis will be used to determine the inflection point of inter-papillary muscle separation at which FMR will recur at 12 months after annuloplasty. Sample sizes are based on previously published data, and on ensuring the ability to detect with high probability, a clinically meaningful presumed benefit for patients undergoing mitral valve repair.

Recruitment to the papillary muscle approximation arm is not based on power analysis as it is only a pilot study.

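### The primary IPMS predictor is not defined: three phases, each at three levels and in up to two modalities, feed one ROC cut-off with no rule for choice, multiplicity or optimism

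*Combined protocol and SAP*

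**What the plan says.** The Protocol Summary and Section 9.0 state the same primary endpoint: whether "pre-operative inter-papillary muscle separation (diastolic, systolic and diastolic-systolic) correlates with FMR severity at 12 months". The three phases are listed together and none is put first.

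Section 9.0 then defines the measurement. "IPMS will be measured at three locations: papillary muscle tips, mid-body and base", and "IPMS is reported in diastole, systole and differences between diastole and systole". This definition appears once under the echocardiographic parameters and again, in the same words, under the cardiac MRI parameters.

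Section 11.0 does not carry these distinctions over. "Pre-operative inter-papillary muscle separation will be measured and is a continuous variable", and "An ROC curve analysis will be used to determine the inflection point of inter-papillary muscle separation" at which FMR recurs at 12 months. The same section gives the primary objective as a correlation with the "6 month and 12 month post-operative FMR grade after undersizing mitral annuloplasty", while the Protocol Summary, Section 2.0 and Section 9.0 fix the primary time point at 12 months.

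Section 3.0 gives the cut-off two roles. It defines the 15 pilot patients who receive PMA with UMA, and it is to be validated by computational modelling on images from the same 125 UMA patients.

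**The concern.** A ROC analysis needs one predictor, and the plan offers many without saying which one is meant. An analyst could compute the association and the ROC curve for every combination and carry forward the strongest. Nothing in the plan prevents this, requires an adjustment, or corrects for it.

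Two things are at stake. First, an association or AUC selected as the best of several is too favourable on average, and so is the accuracy of a cut-off taken from it. Modelling in the same patients cannot remove that optimism, because it uses no new outcome data. Second, the cut-off cannot be applied as written: one patient may lie above it at one level or phase and below it at another, so the pilot criterion has no unique meaning.

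**Working it through.** **Plan's own figures.** The group sizes add up: 50 + 75 = 125 UMA patients, and 125 + 15 = 140. The 125 cannot be re-derived, because Section 11.0 gives no alpha, power, correlation, AUC or dropout.

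**Count.** 3 phases × 3 levels = 9 candidates in one modality; 9 × 2 modalities = 18. One phase is the difference of the other two, so the 18 come from 12 separate measurements.

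**Assumptions.** Two-sided 5% per test, no true effect, equal variances, and correlation r between measurements of 0.5 to 0.9. The documents give none of these.

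**Why one correlation cannot cover all candidates.** If diastolic (D) and systolic (S) values correlate at r, then corr(D − S, D) = √((1 − r)/2), and corr(D − S, S) is its negative. At r = 0.8 this is ±√0.1 = ±0.32, not 0.8. I therefore correlated only the D and S values and computed D − S from them.

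**Chance of at least one nominally significant measure.** The reference for independent tests is 1 − 0.95^k: 14.3% for k = 3, 37.0% for k = 9 and 60.3% for k = 18. Simulated results for r from 0.9 down to 0.5:

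| Candidates | Chance |
|---|---|
| 1 pre-named | about 5% |
| 3 phases, one level and modality | about 11–12% |
| 9, common correlation r | about 23–29% |
| 18, common correlation r | about 35–47% |
| 18, product structure | about 26–48% |

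In the product structure, r is multiplied once for each of phase, level and modality in which two measurements differ. Under that structure the nine-measure figure falls to about 18% at r = 0.9; at r = 0.5 it is about 29%.

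**Null AUC.** Inputs: 125 evaluable patients with no attrition, and the 32.6% one-year recurrence in the Protocol Summary, so 125 × 0.326 ≈ 41 events and 84 non-events. Direction is left free, so an AUC below 0.5 is reflected.

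- One pre-named measure: SD = √(126/(12 × 41 × 84)) = 0.055. The mean is 0.5 + 0.798 × 0.055 = 0.54, and the 95th percentile is 0.5 + 1.96 × 0.055 = 0.61.
- Best of three phases (simulated): mean about 0.57, 95th percentile about 0.63.
- Best of 18 (simulated): mean 0.59–0.61, 95th percentile 0.64–0.66.

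Section 3.0 gives about 36% recurrence instead (125 × 0.36 = 45 events). This leaves the results essentially unchanged.

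**The case against.** **No alpha is claimed, and all three phases are to be reported.** Both are true. A reader might infer that the plan breaches a 5% error rate or sets out to report only the best measure; the documents support neither. What remains is that one cut-off is to be derived and used, and the plan does not say from which measure.

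**Eighteen is a maximum.** The Protocol Summary lists interpapillary muscle dynamics only under pre-operative MRI. The MRI definition in Section 9.0 still refers to an echo plane, so it may be copied text. Against that, Section 9.0 lists papillary muscle separation among the echo measures. Nine is defensible and 18 is an upper count. The three phases need only the endpoint sentence.

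**The 6-month grade might seem to double the count.** It does not add a second ROC outcome, because Section 11.0 defines binary recurrence and the ROC analysis at 12 months only. The 6-month wording is an inconsistency to tidy.

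**The measures are correlated.** This stands: the 60% figure for independent tests is a reference only. Under every correlation examined, the chance remains well above 5%.

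**A best-of-18 AUC near 0.6 overstates the effect of selection.** This stands in part. With direction free, one null measure already averages 0.54, so selection adds about 0.05–0.07. The hypothesis that elevated IPMS is harmful is directional, but no direction is given for the difference measure.

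**Later patients might be steered to an added procedure.** The documents describe use of the cut-off only for the 15-patient pilot; wider use is speculation.

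**Conclusion.** The point holds. The primary predictor is undefined in phase, level and modality, and one in-sample cut-off is to be taken from it without a selection rule, multiplicity control or optimism correction. The firmest figure is the 11–12% chance of a nominally significant result among the three phases alone, about twice the 5% for one named measure. The nine- and 18-measure figures depend on assumed correlations, and the AUC figures also assume full follow-up and 41 events. They illustrate optimism; they do not estimate what this study will show. The choice of measure loses its credibility once outcomes have been examined, so the plan should be amended before then.

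**What to change.** Before any outcome analysis:

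1. Name one phase, one level and one modality as the primary IPMS predictor of 12-month FMR, and state which frames count as diastole and systole. The site of the PMA stitch is not in itself a reason to prefer one level, because the primary question concerns outcome after UMA.
2. Add a rule for patients who lack the chosen modality. Section 9.0 says "Late-Gadolinium enhanced cardiac MRI will be performed on all patients pre-operatively", while the Section 8.0 footnote to the TEE and MRI entries "indicates that both procedures could be performed, or only one of them, depending on what is practically possible". These must be reconciled.
3. Make all other combinations and the 6-month grade secondary, with a max-statistic permutation or Holm adjustment. If the three phases stay co-primary, apply the adjustment to them; a simple Bonferroni level would be 0.05/3 = 0.0167, against 0.05/18 = 0.0028 for all 18.
4. Derive the cut-off on the primary measure only, and report bootstrap optimism-corrected AUC, sensitivity and specificity. If more than one measure is compared, repeat the selection inside each bootstrap sample.
5. Align Section 11.0 with the 12-month primary time point.

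The cost is SAP wording and a bootstrap; no new patients or imaging are needed. The sponsor must commit to one measure in advance, the reported accuracy will look slightly less favourable, and patients without the chosen modality must be handled by the stated rule.

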## 1.0 PROTOCOL SUMMARY

Title	Improving mitral repair for functional mitral regurgitation (IMPROVE-FMR)
Precis	
Functional mitral regurgitation (FMR) can have an adverse impact on the cardiomyopathic left ventricle, by imposing a chronic low-pressure volume overload. Unrepaired FMR increases the risk of congestive heart failure and death. Undersizing mitral annuloplasty (UMA) is the current gold standard for repair of FMR, but its outcomes are poor with 32.6% of patients presenting with clinically significant recurrent FMR at 1 year after the repair, which increases to 58.8% of the patients at 2 years after annuloplasty. Currently, we do not understand why some patients have failure of annuloplasty, while others do not. Lack of mechanistic insights has inhibited an evidence driven approach in optimizing the repairs adequately – resulting in plethora of new sub-valvular techniques, but very few with appropriate scientific justification to be tested in randomized trials.
 
Our team recently performed a retrospective cardiac MRI study in FMR patients and identified that inter-papillary muscle separation (IPMS) is a strong determinant of FMR severity prior to undergoing any repair. Using image-derived computational biomechanical modeling, we reported that when IPMS is elevated, marginal chordal forces restrict parallelization of the leaflet edges and cause higher FMR. We built upon this observation, and performed an ex vivo bench study to demonstrate that IPMS is a strong determinant of repair success as well. In this study, we demonstrated that the MR volume after repair is directly correlated to the pre-operative IPMS. We recently advanced this study further into a chronic swine model, and demonstrated that swine undergoing papillary muscle approximation (PMA) alone or concomitantly with undersizing mitral annuloplasty (UMA), have better valvular function at 3 months after surgery, compared to animals that receive UMA alone. Their valvular kinematics were superior, and so was their ventricular function.
 
In this observational, prospective, non-randomized study in humans with FMR, we seek to investigate the following:
 

• Question 1: Does pre-operative IPMS correlate with the severity of FMR after UMA at 30 days, 6 months and 12 months. We will study this primary objective by conducting pre-operative MRI and echo in patients receiving UMA, and follow them to one year. Secondly, we will use these images from each patient as input to a computational biomechanical model, which will help demonstrate the chordal forces and stresses before repair, after repair and at the follow-up time points. We will recruit a total of 125 patients to this phase of the study.

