
	
 
• Question 2: Does reducing IPMS with a papillary muscle approximation stitch reduce the FMR severity after UMA, by improving valve geometry and biomechanics. We will conduct a pilot study of 15 patients with this approach and investigate their outcomes at 1 year after the surgery.
 

Hypothesis	Elevated IPMS is a risk factor for failure of UMA and recurrence of FMR at 12 months the repair. Reducing IPMS with a papillary muscle approximation stitch can reduce FMR recurrence after UMA.
Objectives	
 
(1) Determine if pre-surgery diastolic IPMS, systolic IPMS and (diastolic-systolic) IPMS correlates with the severity of FMR at immediate post-op, 30 days, 6 months, and 12 months post-UMA.
 
(2) Does IPMS reduction with PMA performed concomitantly with UMA, help in reducing the severity of FMR at immediate post-op, 30 days, 6 months, and 12 months after surgery.
 

Primary Endpoints	The primary endpoint of this study is to investigate if pre-operative inter-papillary muscle separation (diastolic, systolic and diastolic-systolic) correlates with FMR severity at 12 months after surgery with UMA and UMA+PMA.
Secondary Endpoints	
Survival
 
 
• All-cause mortality at discharge, 6 months and 1 year
 
 
Functional Status and Hospitalizations
 
 
• MACE (death, stroke, worsening heart failure (+1 NYHA Class), CHF hospitalization, mitral valve re-intervention at 6 months and 1 year
 
• NYHA classification at 6 months and 1 year
 
• 6-minute walk test at 6 months and 1 year
 
• Readmission rates at 6 months and 1 year
 
 
Physiologic
 
Pre-operative:
 
 
• MRI 
 
- MR severity
 
- Interpapillary muscle dynamics
 
- Left ventricular function
 
- Left ventricular geometry
 
- Left ventricular perfusion and motion defects
 
- Left ventricular scar burden
 
 
 
• Echo (transthoracic and transesophageal) 
 
- MR severity (ERO and regurgitant fraction)
 
 
 

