	
Rationale: The decision to perform mitral valve surgery could be made during the surgery by the surgeon, and these patients would be suitable for this study, but would not be consented prior to their surgery. Thus, in this registry, we will identify such patients for recruitment into this study, as their first research point isn't until 6 months after their surgery.
 
Step 1) Charts will be screened for patients who underwent surgery for the lesion of interest at Emory, who would otherwise be eligible for this study but were not recruited as it was not known if they will need mitral valve surgery.
 
Step 2) Patients who are still within 6 months (<math>\pm</math> 1 month) after the date of their surgery will be contacted after surgery and the study objective will be explained, verbal consent will be obtained and the date to visit Emory will be provided.
 
Step 3) Written consent will be obtained at their 6 month visit, and steps 9 and 10 described in registry # 1 will be performed.
 
Registry # 3: Retrospectively identified patients, who already underwent the standard of care surgery, and were identified after the procedure is completed, and are suitable for recruitment to the study for their post-operative research.
 
Rationale: Historical review of patients between dates 1/1/2004 to present who have undergone mitral valve surgery who were not previously identified in the study. These patients have not been consented prior to their surgery. The purpose is to increase the study sample size in order to gain statistical power for outcome analysis.
 
Step 1) Charts will be screened for patients who underwent surgery between 1/1/2004 to present for the lesion of interest at Emory, who would otherwise be eligible for this study but were not recruited as it was not known if they will need mitral valve surgery or were not recruited as they may have received the surgery prior to study start date.

Sample size	
140 subjects in total at Emory University.
 
Group 1: 125 patients to receive UMA and followed to 12 months, with interim imaging.
 
Group 2: 15 patients to receive UMA with PMA and followed to 12 months, with interim imaging.

	
It is expected that we will recruit ~25 patients per year.
 
Group 3: patients' medical charts will be queried between 2004 – present, number of subject charts are undetermined/unknown.

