## 2.0 OBJECTIVE

The primary objective of this protocol is to investigate if pre-operative inter-papillary muscle separation (IPMS) is predictive of FMR severity at 12 months after undersizing mitral annuloplasty (UMA) to repair functional mitral regurgitation (FMR). Furthermore, whether a cut-off value of pre-operative inter-papillary muscle separation can be established to predict patients who might have failure of UMA.

The secondary objective of this protocol is to investigate if adding papillary muscle approximation (PMA) to UMA is an effective technique in reducing recurrence of FMR at 12 months' post-procedure.

The third objective is to use computational modeling to define the impact that IPMS has on chordal force imbalance, to define the mechanistic basis for repair failure. MRI and echo images from the patients will be used to accomplish this objective.

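### The primary endpoint covers UMA and UMA+PMA, while the primary objective and analysis plan cover UMA only, and the comparison for the PMA objective is not specified

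*Combined protocol and SAP*

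**What the plan says.** The primary endpoint appears in the same words in section 1.0 (Primary Endpoints) and section 9.0. It asks whether pre-operative IPMS "correlates with FMR severity at 12 months after surgery with UMA and UMA+PMA".

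The other statements of the primary question name UMA alone:
- Section 1.0, Question 1 concerns UMA patients: "We will recruit a total of 125 patients to this phase of the study".
- Section 1.0, Objective 1 asks whether IPMS "correlates with the severity of FMR at immediate post-op, 30 days, 6 months, and 12 months post-UMA".
- Section 2.0 asks whether IPMS "is predictive of FMR severity at 12 months after undersizing mitral annuloplasty (UMA").
- Section 11.0 gives the primary objective as the correlation of IPMS with FMR grade after undersizing mitral annuloplasty, and names an ROC analysis to find the cut-off.

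PMA is a separate question. Objective 2 in section 1.0 asks "Does IPMS reduction with PMA performed concomitantly with UMA, help in reducing the severity of FMR", and the secondary objective in section 2.0 is to "investigate if adding papillary muscle approximation (PMA) to UMA is an effective technique in reducing recurrence of FMR". Group 2 is "15 patients to receive UMA with PMA and followed to 12 months, with interim imaging". Section 3.0 says these 15 patients have IPMS above the cut-off. Section 7.2 (Study assignment) says only that selection is not randomized, and section 11.0 says only that the arm is an unpowered pilot.

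**The concern.** An analyst working from section 9.0 would put 140 patients into the primary analysis. One working from sections 2.0 and 11.0 would use 125. The 15 in dispute are not ordinary extra patients. Under section 3.0 they are chosen on the predictor and then given a procedure intended to change what that predictor does. If the procedure works, patients with high IPMS and no recurrence are added, and the association that the study wants to measure is weakened.

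The PMA objective asks about an effect, but section 11.0 names no comparator subset, effect measure or method. UMA alone is the implied reference. Whether that means all UMA patients or only those with high IPMS changes the expected reference rate, and the choice should not be left until outcomes are known.

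**Working it through.** **1. Text side by side.**

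| Place | Patients in the primary question |
|---|---|
| 1.0 Primary Endpoints; 9.0 | UMA and UMA+PMA |
| 1.0 Question 1; 1.0 Objective 1; 2.0; 11.0 | UMA |

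| Place | IPMS rule for PMA patients |
|---|---|
| 3.0 | Above the cut-off |
| Eligibility lists; Group 2; 7.2 Study assignment; 11.0 | Not mentioned |

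Section 3.0 derives the cut-off from the 125 UMA patients. Section 11.0 places 75 of those 125 in the same phase as the PMA patients.

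**2. Headcounts.** 125 + 15 = 140; 50 + 75 + 15 = 140; 50 + 75 = 125. These agree. Section 11.0 gives no AUC, effect size, alpha or power, so the basis of the 125 cannot be reproduced.

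**3. Inputs for the illustrations.** From the documents: 125 UMA and 15 PMA patients, and 32.6% recurrence at 1 year after UMA (section 1.0). Assumed: IPMS normal with equal variance in patients with and without recurrence; AUC 0.65 to 0.75; PMA patients drawn from above the population Youden cut-off; PMA risk equal to a relative risk (RR) times the UMA risk at the same IPMS.

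**4. Crude contrast with all UMA patients, PMA having no effect.** Let d = √2 × Φ⁻¹(AUC). At the Youden cut-off, sensitivity and specificity both equal S = Φ(d/2). Recurrence above the cut-off is 0.326·S / [0.326·S + 0.674·(1 − S)].

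| AUC | d | S | Recurrence above cut-off | Error (minus 32.6%) |
|---|---|---|---|---|
| 0.65 | 0.545 | 0.607 | 42.8% | +10.2 points |
| 0.70 | 0.742 | 0.645 | 46.7% | +14.1 points |
| 0.75 | 0.954 | 0.683 | 51.1% | +18.5 points |

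With the roughly 36% quoted in section 3.0, the errors are about +10, +15 and +19. The error is zero if AUC is 0.50 or if the section 3.0 rule is not applied. Example at AUC 0.70 and RR 0.5: PMA risk is 0.5 × 46.7% = 23.4%. The true difference is 23.4 − 46.7 = −23.3 points, but the crude difference is 23.4 − 32.6 = −9.2.

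**5. Contrast with UMA patients above a cut-off chosen in the same 125.** The Youden search picks a cut-off that makes recurrence above it look too high. In simulation the apparent rates are 48.4%, 52.1% and 56.0%. Subtracting these from the PMA expectations in step 4 gives 42.8 − 48.4 = −5.6, 46.7 − 52.1 = −5.4 and 51.1 − 56.0 = −4.9 points, in favour of PMA.

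**6. Pooling in the primary analysis.** Simulated power, using a two-sided 5% Mann-Whitney test (assumed, since the plan names no test or alpha):

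| AUC | UMA only | Pooled, RR 1.0 | Pooled, RR 0.5 | Pooled, RR 0.25 |
|---|---|---|---|---|
| 0.65 | 79% | 84% | 69% | about 58% |
| 0.70 | 96% | 98% | 93% | 88% |

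**7. Precision.** With 15 PMA patients, the 95% half-width of an IPMS-adjusted risk difference is about 20 to 29 points across these scenarios.

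**The case against.** **By-procedure reading.** The endpoint could mean two correlations, one per procedure, matching the two objectives. No visible text describes such an analysis, and 15 patients all above a cut-off would have a restricted IPMS range. The section 7.1 schematic is not shown in the text reviewed and could settle part of this. The ROC sentence in section 11.0 says only annuloplasty, which the PMA patients also receive. However, it follows an objective limited to undersizing annuloplasty, in a section that lists the two procedures separately.

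**Pilot status.** Section 11.0 calls the arm a pilot, so no efficacy test is expected and the comparator errors are smaller than the imprecision. That stands and limits the stakes. It explains the missing power calculation, but not the missing comparator.

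**Stronger readings that a reader might infer, and that are not supported:**
- *The comparator choice moves the PMA estimate by 10 points or more in either direction.* The error in favour of PMA is about 5 to 6 points at AUC 0.65 to 0.75. It nears 10 only at AUC 0.50, where IPMS predicts nothing and the crude error is zero.
- *Pooling makes the ROC cut-off unstable.* Pooling moves it by more than 0.25 SD in 17 to 23% of simulated studies. Adding 15 ordinary UMA patients does so in 13 to 19%, so this is mostly sampling noise.
- *IPMS adjustment has been shown to remove the bias.* In this model logistic regression is correct by construction. With other risk shapes, average errors reached up to 7 points.
- *The study sequence is impossible.* The final step in section 3.0 and the phases in section 11.0 can coexist if the 50 phase 1 patients supply the cut-off. The documents leave the source unclear but show no timing error.

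**Conclusion.** The point holds as a conflict in the text and a gap in the PMA analysis; no stated number is wrong. The primary endpoint includes patients whom the primary objective and analysis plan leave out, and the PMA objective has no stated comparator subset or method.

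The effect of pooling is usually modest. Power is slightly higher if PMA does nothing, falls by about 3 percentage points at AUC 0.70 and RR 0.5, and falls by about 20 only when a weak predictor (AUC 0.65) is combined with a 75% risk reduction. The comparator matters more. If section 3.0 is applied and IPMS predicts recurrence, the error is about 10 to 19 points against PMA with all UMA patients, and about 5 to 6 in its favour with a same-data cut-off. Under the selection rule modelled, both are within the uncertainty of a 15-patient estimate.

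These sizes rest on assumed AUC, RR and binormal IPMS. Other confounding in a non-randomized comparison could act either way and is not quantified here. The change should be made, because it is cheap and best settled before outcomes are seen.

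**What to change.** 1. In sections 1.0 and 9.0, state the primary analysis set as UMA only, matching sections 2.0 and 11.0, and report UMA+PMA separately.
2. In section 11.0, make the PMA comparison a descriptive risk difference with a 95% CI against UMA patients, adjusted for one named continuous pre-operative IPMS measure. One form is observed PMA recurrence minus the recurrence expected at those patients' IPMS from a model fitted in UMA patients. Do not use as comparator the UMA patients above a cut-off derived from those same patients, unless corrected for optimism. State that the estimate depends on the shape of the IPMS-recurrence model, that residual confounding remains, and that no efficacy test is intended.
3. Reconcile sections 3.0, 7.2 and 11.0 on whether PMA patients are selected by an IPMS cut-off and which patients supply it.

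The cost is wording only, since pre-operative IPMS is already collected. The drawbacks are a wide PMA interval (about 20 to 29 points either side) and reliance on the IPMS model.
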